#### **5.1.3.6 Other Adverse Events**

*Other adverse events commonly reported with idasanutlin included fatigue/asthenia, pyrexia, peripheral edema, headache, dyspnea, dizziness, and chills. These adverse*

events have been of mild severity and controllable with symptomatic treatment and/or nutritional support.

#### 5.1.4 Risk of Overlapping Toxicities

Overlapping toxicities across *idasanutlin* and obinutuzumab are neutropenia and thrombocytopenia (see Table 14). Overlapping toxicities across *idasanutlin* and *rituximab* are neutropenia and thrombocytopenia (see Table 15).

**Table 14 Overlapping Toxicities: Idasanutlin and Obinutuzumab**

Adverse Event	Idasanutlin a 5-Day Dosing (100• 800 mg/day) (n=34)		Obinutuzumab (n=215) b	
	Overall Number of Adverse Events (%)	Grade • 3 Adverse Events (%)	Overall Number of Adverse Events (%)	Grade • 3 Adverse Events (%)
Anemia	24%	24%	16% c	3% d
Neutropenia	27%	27%	36% c	5%• 14% d
Febrile neutropenia	12%	12%	5% d	3% c
Thrombocytopenia	44%	44%	18% d	5%• 8% d
Diarrhea	74%	9%	5%• 8% d	0 d
Nausea	74%	12%	5%• 9% d	0 d
Vomiting	50%	3%	5% d	0 d
Fatigue	38%	3%	13% c	NA

NA = not applicable.

a Data from Phase I single-agent idasanutlin study NP27872; all patients were dosed for 5 days.

b Data from obinutuzumab monotherapy.

c Data from Study BO29563.

d Obinutuzumab Investigator's Brochure.

**Table 15 Overlapping Toxicities: Idasanutlin and Rituximab**

Adverse Event	Idasanutlin a 5-Day Dosing (100•800 mg/day) (n = 34)		Rituximab (n = 356) b	
	Overall Number of Adverse Events (%)	Grade • 3 Adverse Events (%)	Overall Number of Adverse Events (%)	Grade • 3 Adverse Events (%)
Anemia	24%	24%	1%	1%
Neutropenia	27%	27%	11.2%	4.2%
Febrile neutropenia	12%	12%	<1%	<1%
Thrombocytopenia	44%	44%	9.6%	1.7%
Nausea	74%	12%	17.1%	0.3%
Vomiting	50%	3%	6.3%	0.3%

a Data from Phase I single-agent idasanutlin study NP27872; all patients were dosed for 5 days.

b Data from rituximab monotherapy.

### 5.1.5 Management of Specific Adverse Events

During induction, study treatment may be delayed for toxicity for a maximum of 21 days. If study treatment is delayed for >21 days, obinutuzumab *or* rituximab and idasanutlin treatment will be permanently discontinued (see [Table 16](#), [Table 17](#), and [Table 18](#)).

Treatment delays apply to all toxicities described below; dose modifications apply only to toxicities that are considered to be related to idasanutlin. There will be no dose reductions of obinutuzumab *or* rituximab. Idasanutlin dose may be reduced as outlined in [Table 16](#). There will be no more than one dose reduction per treatment cycle. If the idasanutlin dose is reduced, re-escalation is not permitted.

**Table 16 Idasanutlin Dose Reduction Steps**

Initial Dose	Dose Reduction by (mg)		
	Step 1	Step 2	Step 3
100 mg	minus 50 mg	No further reduction a	No further reduction a
150 mg	minus 50 mg	No further reduction a	No further reduction a
200 mg	minus 50 mg	minus 50 mg	No further reduction a
250 mg	minus 100 mg	minus 50 mg	No further reduction a
300 mg	minus 100 mg	minus 50 mg	minus 50 mg
350 mg	minus 100 mg	minus 100 mg	minus 50 mg
400 mg	minus 100 mg	minus 100 mg	minus 50 mg

a When no further idasanutlin dose reduction is possible, the patient will be discontinued from the study.

Guidelines for management of toxicities during induction treatment are provided in Section 5.1.5.1. Guidelines for management of toxicities during maintenance treatment are provided in Section 5.1.5.2.

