### **3.1.6 Post-Treatment and Survival Follow-Up**

Patients who complete treatment or discontinue treatment for reasons other than disease progression will undergo assessments every 3 months during the post-treatment follow-up period, which will continue until disease progression, the start of new anti-lymphoma treatment, or the end of the study (as defined below), whichever occurs first. Patients who experience disease progression will be evaluated for survival status and new anti-lymphoma treatment every 3 months until the end of the study. Details are provided in the schedules of assessments (see [Appendix 1](#) and [Appendix 2](#)).

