## **4.6 PATIENT, TREATMENT, STUDY, AND SITE DISCONTINUATION**

### **4.6.1 Patient Discontinuation**

Patients have the right to voluntarily withdraw from the study at any time for any reason. In addition, the investigator has the right to withdraw a patient from the study at any time. Reasons for withdrawal from the study may include but are not limited to the following:

- Patient withdrawal of consent at any time
- Any medical condition that the investigator or Sponsor determines may jeopardize the patient's safety if he or she continues in the study
- Investigator or Sponsor determines it is in the best interest of the patient
- Patient non-compliance, defined as consistent failure to show up for scheduled visits

Every effort should be made to obtain information on patients who withdraw from the study before the withdrawal. The primary reason for withdrawal from the study should be documented on the appropriate eCRF. However, patients will not be followed for any reason after consent has been withdrawn.

If a patient withdraws consent, this request must be documented in the source documents and signed by the investigator. At the time of withdrawal of consent, the patient will be asked if he or she agrees to be followed for survival information. This agreement must be documented and signed by the investigator. Study personnel may use a public information source (e.g., county records) to obtain information about survival status.

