### **4.6.2 Study Treatment Discontinuation**

Study treatment (obinutuzumab *or rituximab* and idasanutlin) should be permanently discontinued in patients who experience any of the following:

- DLT during *the DLT window* in patients enrolled in the dose-escalation phase
- Anaphylaxis, acute respiratory distress, or Grade 4 IRR
  - If a Grade 3 IRR is recurrent during the second and subsequent cycles, study treatment may be discontinued at the discretion of the investigator, following an individual benefit• risk assessment.
- Any adverse event that leads to a delay of more than 21 days in the start of the next treatment cycle
- Any hematologic adverse event that meets criteria for permanent discontinuation per guidelines provided in Section 5.1.5
- Grade • 3 non-hematologic adverse event that has a reasonable possibility of being related to study treatment and is either life threatening or does not resolve to Grade <2 within 21 days
- Disease progression
- Pregnancy

The primary reason for study treatment discontinuation should be documented on the appropriate eCRF.

Patients who discontinue study treatment will not be replaced, except as outlined below:

- During the dose-escalation phase (Part 1), patients who discontinue study treatment prior to completing Cycle 1 for reasons other than toxicity will be replaced.
- Patients discontinued before having received at least one dose of each component of the combination will be replaced.

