Grade 3 or 4 hematologic toxicity a, b	
For patients who have had one, two, or no prior dose reductions:
 
 
• Withhold study treatment.a
 
• Administer RBCs or platelets as required.
 
• If patient has not already initiated G-CSF, initiate prophylactic G-CSF for current and subsequent cycles.
 
• If improvement to Grade • 2 or baseline • 14 days after the scheduled date for the next cycle, resume obinutuzumab or rituximab at full dose and resume idasanutlin at current dose.
 
• If improvement to Grade • 2 or baseline 15• 21 days after the scheduled date for the next cycle, resume obinutuzumab or rituximab at full dose and resume idasanutlin at a reduced dose according to guidelines in Section 5.1.5 for current and subsequent cycles.
 
• If study treatment is withheld for >21 days, permanently discontinue study treatment.
 
• Permanently discontinue study treatment if any of the following events occur: 
 
Grade 3 or 4 thrombocytopenia of any duration if associated with Grade ≥ 3 bleeding
 
Recurrent Grade 3 or 4 neutropenia associated with fever of > 38°C (> 5 days) or a documented infection despite use of G-CSF and after one idasanutlin dose reduction
 
Recurrent Grade 4 neutropenia or thrombocytopenia lasting more than 7 days despite use of G-CSF (for neutropenia) and after one idasanutlin dose reduction
 
 
 
 
For patients who have had three prior dose reductions or for patients who reach the lowest dose level and no further dose reduction is applicable (see Section 5.1.5):
 
 
• Permanently discontinue study treatment.
 

G-CSF = granulocyte colony-stimulating factor; NHL = non-Hodgkin's lymphoma.

a Treatment delays apply to all toxicities; dose modifications apply only to toxicities that are considered to be related to idasanutlin

b If cytopenia is thought to be caused mainly by NHL infiltration of the bone marrow, the investigator may decide not to modify dose.

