**Table 19 Guidelines for Management of Non-Hematologic Toxicities (cont.)**

Event		Action to Be Taken
		taking idasanutlin and all expelled tablets are still intact, another dose may be given and the second dose noted in the drug log. Otherwise, no replacement dose is to be given.
Dermatologic toxicity		Permanently discontinue rituximab in the event of Stevens-Johnson syndrome or toxic epidermal necrolysis.
Other non-hematologic toxicities (i.e., not described above), excluding alopecia, nausea, and vomiting	Grade 3 or 4	
For patients who have had no prior dose reductions:
 
 
Withhold study treatment.a
 
If improvement to Grade • 1 or baseline, resume obinutuzumab or rituximab at full dose and resume idasanutlin at a reduced dosea for current and subsequent cycles according to guidelines in Section 5.1.5 for current and subsequent cycles.
 
 
For patients who have had one prior dose reduction:
 
Grade 4 events
 
 
Permanently discontinue study treatment.
 
 
Grade 3 events
 
Withhold study treatment.a
 
 
If improvement to Grade • 1 or baseline, resume obinutuzumab or rituximab at full dose and idasanutlin at a reduced dose according to guidelines in Section 5.1.5 for current and subsequent cycles.
 
 
For patients who have had two prior dose reductions or for patients who reach the lowest dose level and no further dose reduction is applicable (See Section 5.1.1.5):
 
Permanently discontinue study treatment.

	Grade 2	
 
Withhold study treatment.a
 
If improvement to Grade • 1 or baseline, resume obinutuzumab or rituximab at full dose and idasanutlin at current dose
 

h = hour; IRR = infusion-related reaction; PML = progressive multifocal leukoencephalopathy; QD = once a day; TLS = tumor lysis syndrome; ULN = upper limit normal.

a Treatment delays apply to all events; dose modifications apply only to events that are considered to be related to any of the study treatment components. Toxicities that occur during the cycle and subside prior to the next cycle should not trigger the suggested dose modifications.

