**Table 20 Guidelines for Management of Toxicities That Occur during Maintenance Treatment**

Event	Action to Be Taken
Hematologic toxicity: Grade 3 or 4	

• Withhold study treatment.

• Administer myeloid growth factors for neutropenia as allowed according to institutional guidelines.

• If improvement to Grade • 2, resume obinutuzumab or rituximab at full dose and idasanutlin at reduced dose.

• If study treatment is withheld for >42 days, permanently discontinue.

Non-hematologic toxicity: Grade • 2	

• Withhold study treatment

• If improvement to Grade • 1 or baseline, administer obinutuzumab or rituximab at full dose and idasanutlin at reduced dose.

• If study treatment is withheld for >42 days, permanently discontinue.

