## Appendix 1 Schedule of Activities for Patients with Follicular Lymphoma (Dose-Escalation and Expansion) (cont.)

- 
- a The screening period starts with the signing of the Informed Consent Form. Results of standard-of-care tests or examinations performed prior to obtaining informed consent and within the defined window may be used as screening and baseline assessments; such tests do not need to be repeated for screening purposes.
- b Patients who complete maintenance treatment or discontinue maintenance treatment prematurely will undergo assessments at EOM.
- c EOI assessments should be performed 6•8 weeks after Day 1 of the last induction cycle. As an exception, patients who discontinue induction treatment prematurely because of an adverse event may undergo EOI assessments 4•8 weeks after their last dose of study treatment.
- d Patients who complete treatment or discontinue treatment for reasons other than disease progression will undergo assessments every 3 months during the post-treatment FU period, which will continue until disease progression, the start of new anti-lymphoma treatment, or the end of the study, whichever occurs first. The first post-treatment FU visit is 3 months after the EOI visit for patients who do not receive maintenance treatment and 3 months after the last dose for patients who receive maintenance treatment. Patients who experience disease progression will undergo limited assessments every 3 months during the survival FU period, which will continue until the end of the study. The end of the study is defined as the time when all enrolled FL patients have completed or discontinued study treatment and all enrolled DLBCL patients have been followed for at least 1 year after they have completed or discontinued study treatment.
- e Informed consent must be documented before any study-specific screening procedure is performed.

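### The Table 16 footnote takes a patient with no idasanutlin reduction left off the study, while Tables 17 and 19 and the follow-up rules stop study treatment only (minor)

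*Combined protocol and SAP*

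**What the plan says.** Table 16 lists the permitted idasanutlin reductions by starting dose. Its footnote is attached to the cells of the 100, 150, 200 and 250 mg rows where no further step exists: "When no further idasanutlin dose reduction is possible, the patient will be discontinued from the study".

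Table 17 (hematologic toxicity) covers the same patient, "or for patients who reach the lowest dose level and no further dose reduction is applicable", points to section 5.1.5, and ends study treatment. Table 19 does the same for other Grade 3 or 4 non-hematologic toxicity: "for patients who reach the lowest dose level and no further dose reduction is applicable (See Section 5.1.1.5".

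Section 4.6.2 lists under treatment discontinuation: "Any hematologic adverse event that meets criteria for permanent discontinuation per guidelines provided in Section 5.1.5". Section 4.6.1, on leaving the study, has an open list ("Reasons for withdrawal from the study may include but are not limited to the following") that does not name exhausted reductions.

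Section 3.1.6 states: "Patients who complete treatment or discontinue treatment for reasons other than disease progression will undergo assessments every 3 months". Appendix 1 footnote c and Appendix 2 footnote b add: "As an exception, patients who discontinue induction treatment prematurely because of an adverse event may undergo EOI assessments", with a window of 4 to 8 weeks after the last dose.

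**The concern.** Leaving the study and stopping treatment are different outcomes in this protocol, and the footnote names the wrong one. Table 17 sends the site to the section that holds Table 16, so a reader who follows the pointer meets the conflicting instruction.

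During induction, a literal reading would remove the patient before the EOI PET-CT on which the primary endpoint rests, and before progression and survival follow-up. The patients lost would be those who tolerated treatment worst, so the missing data would be related to toxicity.

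**Working it through.** This is a comparison of wording. The plan gives no figure for how often reductions run out, so there is none to reproduce.

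**1. Is the trigger the same?** The footnote sits on the cells with no further reduction. Tables 17 and 19 act when a qualifying Grade 3 or 4 toxicity occurs in a patient at the lowest dose level. Both tables also have a count-based trigger (three and two prior reductions respectively), which does not affect the comparison. The trigger is the same in practice.

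**2. Is the consequence the same?**

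| Place | Consequence when no reduction remains |
|---|---|
| Table 16 footnote | Off the study |
| Table 17, lowest-dose clause | Off study treatment |
| Table 19, lowest-dose clause | Off study treatment |
| Section 4.6.2 (hematologic events meeting the 5.1.5 criteria) | Off study treatment |
| Section 3.1.6 | Stopped without progression: assessed every 3 months |
| Appendix 1 note c, Appendix 2 note b | Early stop for an adverse event: EOI assessments still provided for |

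The footnote is the only entry that ends participation.

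**3. Would the patient have been due the EOI scans?** Appendix 1 footnote ff and Appendix 2 footnote jj require at least two induction cycles. Table 16 allows two steps from 200 mg (200 − 50 − 50 = 100 mg) and two from 250 mg (250 − 100 − 50 = 100 mg). Section 5.1.5 allows at most one reduction per cycle. A patient starting at either dose would therefore normally have had at least two cycles and be due the scans. From 100 or 150 mg only one step exists, so this is less certain.

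**4. How would the lost data be handled?** Section 6.4.1 counts as non-responders only patients with no post-baseline tumor assessment. A patient with the CT scan before Cycle 3 but no EOI PET-CT is not explicitly covered. Under section 6.4.3, event-free patients are censored at the last valid assessment for PFS, EFS and DFS, and at the date last known alive for OS. These four endpoints are exploratory.

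**5. How often would the footnote be the rule that applies?** Several rules end study treatment, in those terms, before reductions are exhausted or at the same point:
- Section 5.1.5: a delay of more than 21 days.
- Table 17: after one reduction, recurrent Grade 4 neutropenia or thrombocytopenia lasting over 7 days, or recurrent neutropenia with prolonged fever or infection.
- Table 19, other non-hematologic events: a Grade 4 event after one reduction, or a further Grade 3 or 4 event after two. Two is also the number of steps in the 200 and 250 mg rows.

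Table 17 also lowers the dose only when recovery takes 15 to 21 days; faster recovery resumes the current dose. The footnote will often not be the first rule reached.

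**The case against.** The strongest reply is that the intended action can be recovered. Tables 17 and 19, sections 3.1.6 and 4.6.2 and both schedules agree, and a site would have to set them aside to cause harm. The amendment log reports updates to Tables 17, 19 and 20 and none to Table 16, and the lowest-dose clause in Table 17 is in the italics that mark new text, so the footnote looks like wording left unaligned. The protocol is loose with this phrase elsewhere: the replacement rule for the dose-limiting toxicity window speaks of leaving the study in section 3.1.2 and of stopping treatment in section 4.6.2. The footnote itself does not mention scans or follow-up. Section 4.6.1 bars follow-up only after consent is withdrawn. The appendices say that patients may have EOI assessments in the special window, not that they must.

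All of this stands, and it is why the severity is minor. It does not remove the contradiction: the footnote is current, directive text, and nothing says which instruction prevails.

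A reader might also infer that the primary endpoint is at risk after induction, because Table 20 resumes the antibody "at full dose and idasanutlin at reduced dose" and has no lowest-dose row. The documents do not support that. It is an inference that Table 16 governs maintenance and consolidation: section 5.1.5 cites it in the sentence on delays during induction, and Table 7 leaves the post-induction idasanutlin dose to the sponsor. Even if it does govern them, EOI assessments fall 6 to 8 weeks after Day 1 of the last induction cycle and post-induction treatment starts at 8 weeks (± 1 week), so the EOI PET-CT would normally be done.

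**Conclusion.** The footnote is wrong as written and should be corrected; the severity is minor. The contradiction rests on text alone and is certain. The consequence is conditional: a patient must exhaust reductions during induction before another stopping rule applies, and the site must follow the footnote over the other provisions. The documents give no probability for either. The effect is probably small, and no number can be put on it.

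Two figures might tempt a reader as measures of impact, and neither is one. The first is the chance of exactly 22 complete responses in 40, the smallest count whose exact 90% interval excludes 40%. It is 12.6% at a true rate of 55%. It says nothing about whether a patient is lost through the footnote or would have been a responder, and section 6.4.1 plans estimation with no pass/fail test. The second is that the selected dose in Appendix 11, Table 3 falls on a footnoted row in 5 of 7 scenarios. Each entry is a selected dose recommended in 33% to 52% of simulated trials, and scenarios 1 and 7 share the same true toxicity, so the count is not a probability that the footnote will apply.

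**What to change.** In the Table 16 footnote, replace the consequence with: *the patient will be discontinued from study treatment*. Add one sentence: the patient remains in the study for the scheduled EOI assessments (scans if at least two induction cycles were received) and for section 3.1.6 follow-up. At the same time, correct the Table 19 pointer to section 5.1.1.5 (Infections), which appears to be a slip for 5.1.5.

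The cost is one changed phrase, one added sentence and one cross-reference. The visits and scans are already in Appendices 1 and 2.

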### 5.1.5.1 Toxicities during Induction Treatment Hematologic Toxicities

Table 17 provides guidelines for management of hematologic toxicities that occur during induction treatment, with the exception of Days 8 and 15 of Cycle 1. Table 18 provides guidelines for management of hematologic toxicities that occur on Days 8 and 15 of Cycle 1, when patients are to receive treatment with obinutuzumab only. Hematologic toxicity is defined as neutropenia, anemia, or thrombocytopenia. Lymphopenia is not considered hematologic toxicity but an expected outcome of therapy.

**Table 17 Guidelines for Management of Hematologic Toxicities That Occur during Induction Treatment (Except for Days 8 and 15 of Cycle 1)**

Event	Action to Be Taken
Grade 3 or 4 hematologic toxicity a, b	
For patients who have had one, two, or no prior dose reductions:
 
 
• Withhold study treatment.a
 
• Administer RBCs or platelets as required.
 
• If patient has not already initiated G-CSF, initiate prophylactic G-CSF for current and subsequent cycles.
 
• If improvement to Grade • 2 or baseline • 14 days after the scheduled date for the next cycle, resume obinutuzumab or rituximab at full dose and resume idasanutlin at current dose.
 
• If improvement to Grade • 2 or baseline 15• 21 days after the scheduled date for the next cycle, resume obinutuzumab or rituximab at full dose and resume idasanutlin at a reduced dose according to guidelines in Section 5.1.5 for current and subsequent cycles.
 
• If study treatment is withheld for >21 days, permanently discontinue study treatment.
 
• Permanently discontinue study treatment if any of the following events occur: 
 
Grade 3 or 4 thrombocytopenia of any duration if associated with Grade ≥ 3 bleeding
 
Recurrent Grade 3 or 4 neutropenia associated with fever of > 38°C (> 5 days) or a documented infection despite use of G-CSF and after one idasanutlin dose reduction
 
Recurrent Grade 4 neutropenia or thrombocytopenia lasting more than 7 days despite use of G-CSF (for neutropenia) and after one idasanutlin dose reduction
 
 
 
 
For patients who have had three prior dose reductions or for patients who reach the lowest dose level and no further dose reduction is applicable (see Section 5.1.5):
 
 
• Permanently discontinue study treatment.
 

G-CSF = granulocyte colony-stimulating factor; NHL = non-Hodgkin's lymphoma.

a Treatment delays apply to all toxicities; dose modifications apply only to toxicities that are considered to be related to idasanutlin

b If cytopenia is thought to be caused mainly by NHL infiltration of the bone marrow, the investigator may decide not to modify dose.

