### **3.1.2            Dose-Escalation Phase (Part 1)**

The purpose of the dose-escalation phase (Part 1) is to identify the RP2D *and regimen* for idasanutlin when combined with a fixed dose of 1000 mg of obinutuzumab in patients with R/R FL and *the RP2D for idasanutlin when combined with 375 mg/m^2 of rituximab in patients with R/R DLBCL*. The RP2D will be based on MTD of idasanutlin when combined with a fixed dose of obinutuzumab *or with 375 mg/m^2 of rituximab*, but will also include all safety data during treatment. *There could be two different RP2Ds and/or regimens dependent on the combinations of idasanutlin plus obinutuzumab or idasanutlin plus rituximab.*

During the escalation phase, approximately 9• 40 patients will be enrolled in dosing groups of 3• 6 patients each and will be treated at escalating doses of idasanutlin in accordance with the treatment regimen and dose-escalation rules described in Section 3.1.2.2.

Patients will be closely monitored for adverse events during a DLT assessment window, defined as the first treatment cycle *for Regimen A and the first two treatment cycles (one cycle of idasanutlin combination treatment) for patients enrolled in bridging cohort(s) in which idasanutlin will start at Cycle 2 (Regimen B)*. See Section 3.1.2.2 for treatment regimens. Adverse events meeting the criteria for DLT, as defined below (see Section 3.1.2.1), will be reported to the Sponsor within 24 hours (see Section 5.4.2).

Patients experiencing a DLT during the *DLT window* will permanently discontinue study treatment.

Patients who discontinue from the study prior to completing the DLT assessment window for reasons other than a DLT will be considered non-evaluable for dose-escalation decisions and MTD assessments and will be replaced by an additional patient at that same dose level who has not been previously treated in the study. Patients who miss one or more doses of obinutuzumab, *rituximab*, or idasanutlin during the DLT assessment window for reasons other than a DLT will also be replaced.

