### 3.1.2.1 Definition of Dose-Limiting Toxicity

In this study, a DLT is defined as at least one of the following events occurring during the first cycle (*or the first two cycles in the bridging cohorts for patients with FL who start idasanutlin at Cycle 2*) of treatment and assessed by the investigator as not clearly related to the patient's underlying disease:

- *Any Grade 5 adverse event unless unequivocally due to the underlying malignancy or extraneous causes*
- Adverse event of any grade that leads to a delay of more than 14 days in the start of the next treatment cycle
- Grade 3 or 4 non-hematologic adverse event, with the following exceptions:
  - Grade 3 or 4 IRRs
    - Note that IRRs are not dose-dependent events. They may occur even after a small amount of drug has been administered.
    - Grade 3 diarrhea that responds to adequate therapy within 48 hours
    - Grade 3 nausea or vomiting that occurs in the absence of premedication and responds to adequate therapy within 72 hours
- *Any increase in hepatic transaminase > 3 • baseline and an increase in direct bilirubin > 2 • ULN, without any findings of cholestasis or jaundice or signs of hepatic dysfunction and in the absence of other contributory factors (e.g., worsening of metastatic disease or concomitant exposure to known hepatotoxic agent or of a documented infectious etiology) is suggestive of potential drug induced liver injury (according to Hy's Law) and will be considered a DLT*
- Hematologic adverse events that meet any of the following criteria:
  - Grade 3 or 4 neutropenia in the presence of sustained fever of >38°C (lasting >5 days) or a documented infection
  - Grade 4 neutropenia lasting >7 days
  - Grade 3 or 4 thrombocytopenia *if associated with Grade ≥ 3 bleeding*
  - Grade 4 thrombocytopenia lasting >7 days

Other toxicities that are considered clinically relevant and related to study treatment as determined by the investigator and the Medical Monitor may also be considered DLTs.

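### Tables 17 and 18 do not exempt the Part 1 DLT window, so Table 17 tells sites to re-dose after four kinds of first hematologic event that Sections 3.1.2 and 4.6.2 make a permanent stop

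*Combined protocol and SAP*

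**What the plan says.** **The stop rule.** Section 3.1.2 says that a Part 1 patient with a DLT in the assessment window "will permanently discontinue study treatment". Section 4.6.2 repeats this as the first item in a list where any one item is enough. A separate item in that list points to the hematologic discontinuation criteria of Section 5.1.5.

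**What counts as a DLT.** Section 3.1.2.1 asks for neither recurrence nor an earlier dose reduction. Its hematologic criteria are:

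- "Grade 3 or 4 neutropenia in the presence of sustained fever of" more than 38 °C for over 5 days, or with a documented infection
- "Grade 4 neutropenia lasting >7 days"
- "Grade 4 thrombocytopenia lasting >7 days"
- Grade 3 or 4 thrombocytopenia with bleeding of Grade 3 or worse

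A further criterion, not limited to hematologic events, is "Adverse event of any grade that leads to a delay of more than 14 days in the start of the next treatment cycle".

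**What Table 17 says.** For Grade 3 or 4 hematologic toxicity in a patient with at most two earlier reductions, sites withhold treatment. If recovery comes within 14 days of the scheduled next cycle, the antibody is restarted "at full dose and resume idasanutlin at current dose". If it takes 15 to 21 days, sites "resume idasanutlin at a reduced dose according to guidelines in Section 5.1.5 for current and subsequent cycles". Holds beyond 21 days, and thrombocytopenia with Grade 3 or worse bleeding, are permanent stops. For prolonged Grade 4 cytopenia the permanent stop is "Recurrent Grade 4 neutropenia or thrombocytopenia lasting more than 7 days despite use of G-CSF (for neutropenia) and after one idasanutlin dose reduction". The line for febrile or infected neutropenia carries the same conditions: recurrence, despite G-CSF, after one reduction.

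**The concern.** Table 17 names Days 8 and 15 of Cycle 1 as its only exclusion. The rest of Cycle 1, which is the Regimen A DLT window, is therefore inside it. So is Cycle 2 of Regimen B, the only cycle in that regimen's window that includes idasanutlin. Sections 4.3.2 and 5.1 send sites to this part of the protocol for dose modification, delay and discontinuation.

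A site that follows the table literally would re-dose a patient who has just had a DLT, at the same idasanutlin dose if recovery comes within 14 days. That patient should be off treatment.

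The events are foreseeable. Section 1.4 names thrombocytopenia and neutropenia as the main DLTs in the earlier solid-tumor study. Table 14 reports Grade 3 or worse thrombocytopenia in 44% and neutropenia in 27% of 34 patients on 5-day idasanutlin. Those are not DLT rates, but they show that cytopenia is the expected toxicity.

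**Working it through.** The plan states no figure on this point, so the check sets each DLT criterion that a hematologic event can meet (Section 3.1.2.1) beside the Table 17 action for a first event. The patient is assumed to be in the DLT window with a dose reduction still available. Under Table 16 that includes a patient at the 100 mg starting dose, who can go down by 50 mg.

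| First event in the window | Sections 3.1.2 and 4.6.2 | Table 17 | Agree? |
|---|---|---|---|
| Grade 3/4 neutropenia with fever over 5 days or documented infection | Stop | Hold, then resume; stop only on recurrence after a reduction | No |
| Grade 4 neutropenia over 7 days | Stop | Hold, then resume; stop only on recurrence after a reduction | No |
| Grade 4 thrombocytopenia over 7 days | Stop | Hold, then resume; stop only on recurrence after a reduction | No |
| Grade 3/4 thrombocytopenia with Grade 3 or worse bleeding | Stop | Stop | Yes |
| Hematologic delay of 15–21 days | Stop (over 14 days) | Resume at a reduced dose | No |
| Hematologic delay over 21 days | Stop | Stop | Yes |

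**Count.** There are 4 hematologic DLT criteria, of which 3 conflict and 1 agrees. The delay criterion splits: days 15–21 conflict and later days agree. Conflicting events: 3 + 1 = 4.

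**Search for an exemption.** The text of Section 5.1.5 allows a delay of up to 21 days in induction and sets no 14-day limit for the DLT window. Table 16, Table 17 and the Table 17 footnotes do not mention DLTs. Table 18, which covers Days 8 and 15 of Cycle 1, has no exemption either. It withholds obinutuzumab until fever and infection, or low platelets and bleeding, resolve, and sends events still present on Day 1 of Cycle 2 to Table 17.

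**Which rule governs.** Section 4.6.2 lists the DLT stop and the Section 5.1.5 criteria as separate triggers, and either is sufficient. An event that fails the Table 17 stop criteria but is a DLT must still lead to discontinuation. The DLT rule therefore prevails on a full reading, but Table 17 does not say so.

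**The case against.** The best reply is that the protocol already settles the matter. Two sections state the stop outright, and Section 5.1.5 is general guidance for both parts of the study. On that view only a cross-reference is missing. That the DLT rule governs is accepted. But Table 17 is not silent on these events: it gives an explicit action, and that action is the opposite one. The Version 4 rationale of changes also records that the discontinuation rules in Table 17 were updated when the DLT criterion for thrombocytopenia with bleeding changed. The sponsor aligned the table with one hematologic DLT criterion, and the other three remain unaligned.

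Other points stand in part:

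- **The recurrence lines cannot operate inside the window.** They presuppose an earlier reduction, and the window holds one idasanutlin cycle. This is right. The conflict comes from the hold-and-resume steps; the recurrence lines matter because they leave no permanent stop for a first event.
- **Safeguards lower the risk.** Idasanutlin is given only on Days 1–5, re-dosing waits for recovery, and DLTs must reach the Sponsor within 24 hours. These make an error less likely but do not correct the table.
- **Disease-related cytopenias are not DLTs.** Section 3.1.2.1 leaves out events clearly due to the lymphoma, and those properly stay under Table 17. A fix that cites that definition keeps the limit.
- **Table 19 shows a similar pattern** for other Grade 3 or 4 non-hematologic events. This is a reason to extend the fix.

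**Conclusion.** The inconsistency is real. Of the four hematologic DLT criteria, three conflict with Table 17 at first occurrence, and so does the 15-to-21-day part of the delay criterion, making four conflicting events. The conclusion assumes that the event meets the full Section 3.1.2.1 definition, including the limit on disease-related events, and that a dose reduction is still available; otherwise Table 17 stops treatment as well.

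The consequence is for patient safety. The DLT count in the dose-escalation model is not affected. The documents do not say what share of DLTs these events would make up, so no number of patients is claimed. The governing rule in Section 4.6.2 and the 24-hour report keep the point from being more serious, but the table should be corrected.

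**What to change.** Add one footnote to Tables 17 and 18, along these lines:

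> In Part 1, an event in the DLT window that meets the Section 3.1.2.1 definition requires permanent discontinuation under Sections 3.1.2 and 4.6.2. The steps for holding and resuming, including the reduced-dose step for recovery at 15 to 21 days, do not apply to it.

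Placing the same sentence on Table 19 would deal with the similar pattern there.

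The cost is one sentence per table. Doses, sample size, the DLT definition and the escalation model stay as they are. Nothing changes for expansion patients or for Part 1 patients who have passed the DLT window.
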